#### 5 trial population and descriptive analyses

Summary of flow of trial participants through the trial and baseline stratification, demographic and clinical characteristics of each group.

## 5.1 Representativeness of Study Sample and Patient Throughput

**Figure 1** shows the flow of participants through each stage of the trial, including numbers of participants randomly assigned, receiving intended treatment, completing the study protocol, and analysed for the primary outcome, following the appropriate guideline (e.g. CONSORT). Information on the number of patients screened and found to be ineligible because they meet the exclusion criteria will also be reported.

\* Full adherence in the intervention group is defined as receiving a minimum of 4 physiotherapy sessions and partial adherence is receiving at least one physiotherapy session (i.e. starting the treatment)

Figure 1 The CONSORT flowchart.

#### 5.2 Withdrawals

The number (and percentage) of withdrawal reasons will be presented by treatment arm. Details of each withdrawal will also be investigated, including their days on the trial, site, last questionnaire completed and whether they have their primary outcome available for analyses. (see table 7 and 8 in AFTER\_SAP\_DDT\_V1.0\_18Aug2022). Any deaths (and their causes) will be reported separately (see table 12 in the AFTER\_SAP\_DDT\_V1.0\_18Aug2022).

#### 5.3 Baseline Characteristics

Baseline comparability between two treatment groups (supervised rehabilitation and self-directed rehabilitation) will be investigated. Numbers (with percentages) for binary and categorical variables and mean (and standard deviation),

or median (with lower and upper quartiles) for continuous variables will be presented; there will be no tests of statistical significance nor confidence intervals for differences between randomised groups on any baseline variable (see Table 5 in AFTER\_SAP\_DDT\_V1.0\_18Aug2022).

#### 5.4 Unblinding

AFTER is not a blinded trial.

# 5.5 Treatment Compliance with Details of Intervention

A summary of treatment received (supervised rehabilitation and self-directed rehabilitation) will be provided by treatment arm. Compliance to the supervised rehabilitation treatment is defined as receiving a minimum of 4 physiotherapy sessions and partial compliance is receiving at least one physiotherapy session (i.e. starting the treatment). Compliance will be summarised as full compliance and partial compliance by treatment arm. The reasons for participants who did not receive the treatment that they were allocated will be also summarised by treatment arm (see table 6 in AFTER\_SAP\_DDT\_V1.0\_18Aug2022). Full details of intervention delivery will be reported in line with the TIDieR checklist for reporting complex interventions (8).

## 5.6 Reliability

To ensure consistency, validation checks of the data will be conducted. This will include checking for duplicate records, checking the range of variable values and validating potential outliers where possible (referring back to sites if necessary). As the data is collected electronically, many of these checks will be implemented automatically as part of the data entry procedure and data collection instruments have been validated prior to data entry commencing. Calculations and processes performed by a computer program, including the construction of derived data, will be checked. A sample of 15 participants will be randomly selected from all randomised participants (around 5% of the total planned sample size) for the check. Algorithms and calculations that are performed by a computer program will be checked and validated manually for the 15 selected participants.

For each variable, missing value codes will be checked for consistency and the proportion of missing values per variable will be presented. Patterns of missing data will be explored.

#### 6 Analysis

#### 6.1 Outcome Definitions

#### 6.1.1 Primary outcome

The primary outcome is patient-reported ankle-related symptoms and function at 6 months after randomization measured by completion of the Olerud and Molander Ankle Score (OMAS) (9). The OMAS is a 9-item questionnaire which is completed directly by the participant (0-100, with higher scores indicating better function). The OMAS has been the primary outcome for a number of other ankle fracture trials, including NIHR HTA trials. (7, 10)

## 6.1.2 Secondary outcomes

**Ankle Function:** measured by completion of the Olerud and Molander Ankle Score (OMAS) at baseline, 2 and 4 months after randomization.

Health-related quality of life: assessed using the EuroQol 5 Dimensions (EQ-5D-5L) score (11). The EQ-5D-5L is a validated, generalised and standardised instrument comprising a VAS measuring self-rated health and a health status instrument, consisting of a five-level response (no problems, some problems, moderate problems, severe problems and unable) for five domains related to daily activities; mobility, self-care, usual activities, pain and discomfort, and anxiety and depression. Responses to the health status classification system are converted into an overall score using a published utility algorithm for the UK population. The EQ-5D health status scale ranges from negative scores reflecting a patient's quality of life being worse than death, and 0 [death] to 1 [perfect health]. A respondent's EQ-VAS gives self-rated health on a scale where the endpoints are labelled 'best imaginable health state' (100) and 'worst imaginable health state' (0). This is measured at baseline, 2, 4 and 6 months after randomization.

**Pain:** assessed using the sub-scales of the OMAS and EQ-5D-5L. This is measured at baseline, 2, 4 and 6 months after randomization.

**Physical function**: assessed using PROMIS Physical Function (12). Patient Reported Outcome Measurement Information System (PROMIS) questionnaires are administered electronically, via a Computer Adaptive Test (CAT),

which are dynamic tests based on Item Response Theory (IRT). A mathematical model adapts the sequential questions asked based on a participant's previous response. A tailored set of questions is therefore asked from a large item pool. Participants are typically asked 4 to 6 questions. PROMIS instruments are scored from 0 to 100 with 50 points representing the mean score for the US general population, higher scores indicate better function. Participants who have not completed the online questionnaire or who have no internet access will be able to complete a paper-based version of the PROMIS questionnaire with 4-items (PROMIS Physical Function - Short Form 4a) via postal follow up. If a participant needs to be contacted directly by phone to complete their follow up, they will be asked the PROMIS Physical Function CAT questionnaire as the central site team can directly enter patient responses on their behalf. This is measured at baseline, 4 and 6 months after randomization.

**Self-efficacy**: assessed using the Self-Efficacy Exercise Score (13). The score measures a participant's judgment of their confidence to carry out exercise. The questionnaire has 9-items specifically about the ability to continue to exercise despite barriers. The participant scores their confidence level from 0 (not confident) to 10 (very confident), if they were to exercise 3 times per week for 20 minutes during each of the nine situations presented. The overall scores range 0 to 90, with higher scores indicating greater confidence to exercise. This is measured at baseline, 4 and 6 months after randomization.

**Exercise adherence**: assessed using patient reported exercise frequency. This is measured at 2, 4 and 6 months after randomization.

**Complications:** fracture and treatment complications will be recorded, but particular note will be made of complications related to the interventions. This is measured at 2, 4 and 6 months after randomization.

**Resource use:** patient reported resource use and information on hospital treatments and appointments will be collected. This will include consultations with primary and secondary care, prescribed and over-the-counter pain medication use, additional physiotherapy and hospital admission, self-funded health and social care, out-of-pocket expenses, and work absence. This is measured at 2 and 6 months after randomization.

## 6.2 Analysis Methods

## 6.2.1 Primary outcome analysis

The OMAS at 6 months is the primary outcome. Raw summary statistics (mean and standard deviation) will be calculated and reported by treatment arm for each time point.

The treatment difference between the two groups (self-directed rehabilitation and supervised rehabilitation) will be analysed using a mixed effect linear regression model. The OMAS at all follow-up time points will be the dependent variable (panel data) and the independent variable will be the interaction between treatment group and follow-up time points. This model will adjust for stratification factors of randomization (recruitment centre and initial fracture management (operative vs non-operative)), age in years, and sex at birth as fixed effects in the model.

Sensitivity analyses will be conducted to check the robustness of the analysis results. The analyses will include a partially-adjusted model, per protocol analysis and CACE analysis. A partially-adjusted model will only include baseline OMAS as its sole adjustment variable. Per-protocol analysis will only include participants at least partially compliant in the supervised rehabilitation arm to their allocated treatment (1 or more physiotherapy sessions in supervised rehabilitation arm), and will be conducted for the adjusted model. The per-protocol analysis will also exclude participants who did not receive the self-directed rehabilitation materials when allocated to self-directed rehabilitation.

Complier Average Causal Effect (CACE) analysis:

CACE analysis seeks to compare outcomes for individuals in the intervention condition who complied with treatment with individuals in the control group who would have complied with treatment given the opportunity to do so. The two treatment groups for the AFTER trial are supervised rehabilitation (intervention) and self-directed rehabilitation (control).

Participants in the intervention arm will be defined as non-compliers to the control arm if they have not met the adherence definition: Full compliance is defined as receiving a minimum of 4 physiotherapy sessions. However, it is unlikely for participants in the control arm to crossover to the intervention arm, therefore the per-protocol analysis

will mostly exclude non-compliers in the intervention arm that may result in estimation bias. CACE looks at compliers in the intervention arm and would-be compliers in the control arm (i.e. the participants in the control arm who would comply to the treatment if they were assigned to the intervention arm) (14). The CACE analysis will be done using a two-stage regression model (14-16):

Stage 1: Predict treatment compliance using treatment allocated. Treatment received (compliance) by participants will be used as an instrumental variable (IV) for treatment allocated. A mixed model, with the independent variable as treatment allocation and the dependent variable as treatment compliance, will run, adjusting for baseline OMAS and initial fracture management. The coefficient estimated for treatment allocation will be used to predict treatment compliance in both intervention and control arm.

Stage 2: Use predicted treatment compliance to represent treatment allocation. A mixed effect model will be run with the dependent variable as OMAS scores and independent variable as predicted treatment compliance and follow-up timepoint interaction. The random effect of the model will be recruitment centre and the model will adjust for fracture management and baseline OMAS score. The Stata command "ivregress" can perform the two-stage analysis together.

For fully adjusted (as per primary outcome analysis) and non-adjusted model, the process will be the same with different variables being adjusted.

The treatment effect for OMAS at 6 months (ITT) and sensitivity analyses results will be presented together in one table for comparison (see table 9 in AFTER\_SAP\_DDT\_V1.0\_18Aug2022). They will be reported alongside 95% confidence intervals and p-values calculated using clustered standard error to account for serial correlations. Mixed model assumptions will be assessed using residual plots. In case we have a skewed variable, we will consider transforming or using bootstrapping methods.

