#### 3.8 Statistical Analysis Outline

The primary analysis population will be the intention-to-treat population (ITT), that is participants will be analysed in the group in which they were randomised regardless of what treatment they received. The analyses will be repeated for the per protocol (PP) population. The per protocol population will exclude participants who did not receive the allocated treatment and participants with major protocol deviations, this will be finalised using blinded data prior to

the final datalock. Standard descriptive statistics will be used to describe the demographics between the treatment groups reporting means and standard deviations or medians and interquartile ranges as appropriate for continuous variables and numbers and percentages for binary and categorical variables. Standard statistical summaries and graphical plots will be presented for the primary outcome measure and all secondary outcome measures.

The OMAS score at 6 months is the primary outcome in this study and will be compared between treatment groups as the dependent variable in a mixed-effects linear regression model including outcome information at intermediate time-points. This model will adjust for stratification factors (initial fracture management; operative or non-operative) and baseline OMAS score. A random effect will be included to account for heterogeneity due to recruitment centres. The treatment effect will be based on adjusted mean differences at 6 months and will be reported together with their 95% confidence intervals.

We will also undertake a Complier Average Causal Effect (CACE) analysis which essentially compares the "compliers" in each group. The CACE analysis will be undertaken using the definition of full compliance in the intervention group – defined as receiving a minimum of 4 physiotherapy sessions. Partial compliance is receiving at least one physiotherapy session (i.e. starting the treatment), which will be used in the per-protocol analysis. This will provide supporting evidence to any findings from the principal analysis. Subgroup analysis by surgical vs non-surgical treatment of the fracture will be undertaken, using a treatment by subgroup interaction term and will be presented using forest plots.

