## 4.2 Definition of Analysis Populations

The primary analysis population will be the intention-to-treat population (ITT), that is participants will be analysed in the randomised group in which they were allocated to regardless of what treatment they received. Patients with baseline outcome and at least one post-randomization outcome will be included in the analysis.

[figure not shown]
The analyses will be repeated for the per protocol (PP) population. The per protocol population will exclude participants who did not receive the allocated treatment and participants with major protocol deviations.

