## 6.2.2 Secondary outcome analysis

Summary statistics by treatment arm will be computed for EQ-5D-5L, pain, PROMIS, self-efficacy, exercise adherence and complications. Similar methods to the primary outcome will be used to analyse continuous secondary outcomes, with their mean and standard deviation or median and interquartile range reported. Only the intention to treat (ITT) population will be used for secondary outcome analysis (see table 10 in AFTER\_SAP\_DDT\_V1.0\_18Aug2022).

OMAS at baseline, 2 and 4 months: The treatment difference for the OMAS at other follow-up time points will be the adjusted difference at these time points taken from the same model used for the primary outcome analysis.

EQ-5D-5L utility score (at baseline, 2,4 and 6 months): will be calculated by the ED-5D-5L mapping function (17) and range from -0.594 to 1. If a participant dies before end of follow-up, their utility score will be imputed as 0. Similar to the analysis for primary outcome, a mixed effect model with recruitment centre as random effect and adjust for stratification factor (initial fracture management) and baseline utility score. The independent variable of the model will be treatment and follow-up time point interaction. This model will adjust for stratification factors of randomization (recruitment centre and initial fracture management (operative vs non-operative), as well as important prognostic factors of age and sex. Results for treatment effect at each of the follow-up timepoint will be presented with confidence intervals and p-values.

EQ-5D-5L VAS score (at baseline, 2, 4 and 6 months): is a score ranges from 0 to 100, with better score indicating better health. The analysis for the VAS score will be the same as with the EQ-5D-5L utility score, but adjusting for baseline EQ-5D-5L VAS score.

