#### 6.4 Pre-specified Subgroup Analysis

Subgroup analysis will be conducted on fracture management (surgical vs non-surgical). The purpose of subgroup analyses is to investigate if the estimated treatment effects are relatively consistent across subgroup and for this extent will be viewed as exploratory.

The analysis population will be divided into their respective subgroup, and if there are too few participants in one subgroup (<=15) or one treatment arm of a subgroup (<=5), the analysis of that subgroup is likely to be biased due to small number of samples. In that case, that subgroup will be combined with other subgroups with more participants or the subgroup analysis will not be conducted.

Linear regression will be performed for each subgroup analysis. The model will include a treatment-subgroup interaction term to capture the effect of subgroups. The estimated treatment difference and confidence intervals will be reported and presented in forest plots. The results will be presented in forest plots with 95% confidence interval.

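### Sections 3.8 and 6.2.1 of the SAP specify the primary OMAS model differently: they disagree on baseline OMAS, age, sex and whether centre is fixed or random

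*SAP*

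**What the plan says.** Section 3.8 outlines a mixed-effects linear regression for OMAS that uses the intermediate time points. On covariates it says: "This model will adjust for stratification factors (initial fracture management; operative or non-operative) and baseline OMAS score". On centre it says: "A random effect will be included to account for heterogeneity due to recruitment centres". Age and sex do not appear.

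Section 6.2.1 gives the methods for the same analysis. It has OMAS at all follow-up time points as the dependent variable and a treatment-by-time interaction. The adjustment covers "recruitment centre and initial fracture management (operative vs non-operative)), age in years, and sex at birth as fixed effects in the model". Baseline OMAS is not in that list. The model is called mixed, but no random effect is named for centre or for participant.

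Elsewhere the SAP says:
- Section 6.2.1, sensitivity analyses: "A partially-adjusted model will only include baseline OMAS as its sole adjustment variable".
- Section 6.2.1, CACE stage 2: "The random effect of the model will be recruitment centre and the model will adjust for fracture management and baseline OMAS score".
- Section 4.2, analysis set: "Patients with baseline outcome and at least one post-randomization outcome will be included in the analysis".
- Section 6.2.2, EQ-5D utility, introduced as similar to the primary analysis: "a mixed effect model with recruitment centre as random effect and adjust for stratification factor (initial fracture management) and baseline utility score". The PROMIS model is worded in the same way. Both paragraphs then name centre again among the stratification factors to adjust for.
- Section 6.4: "Linear regression will be performed for each subgroup analysis", with a treatment-by-subgroup interaction.

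**The concern.** The primary model should be fixed by one description. Here, two competent statisticians could each fit a different model and both claim to follow the SAP. That matters for three of the SAP's own provisions. Section 4.1 sets a 1% level for analyses that are not pre-specified, so it must be clear which model is. Section 7 has an independent statistician repeat the analyses, and a discrepancy could come from the text rather than from an error. The per-protocol analysis and the fully adjusted CACE analysis both refer back to the primary adjusted model and so inherit the ambiguity. An open choice of model also leaves room to settle it after results are seen.

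Read literally, 6.2.1 also produces an odd structure. The partially adjusted sensitivity model contains a covariate that the full model lacks, so the two are not nested. Participants without a baseline OMAS would be left out of an analysis that does not use baseline OMAS. A variable already collected at baseline (Table 1) would add nothing to the precision of the primary estimate, and chance baseline imbalance in it would go uncorrected.

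**Working it through.** **Side-by-side reading of the primary model**

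| Element | Section 3.8 | Section 6.2.1 |
|---|---|---|
| Baseline OMAS | included | not listed |
| Fracture management | included | included, fixed |
| Centre | random | fixed |
| Age, sex | not listed | included, fixed |
| Random effect named | centre | none |

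The two agree on fracture management alone. The CACE stage 2 model and the EQ-5D and PROMIS models side with 3.8 on baseline score and random centre. The EQ-5D and PROMIS paragraphs side with 6.2.1 on age and sex. No sentence settles precedence.

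**The plan's sample size (section 3.3)**

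Inputs: difference 8, SD 21, two-sided 5%, 90% power, 15% loss.

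- Normal approximation: n per arm = 2 × (1.960 + 1.282)² × 21² / 8² = 144.8, so 145.
- Two-sample t-test: 145.8, so 146 per arm and 292 in total, as stated.
- Loss to follow-up: 292 / 0.85 = 343.5, so 344, as stated.
- SE at 146 per arm = 21 × √(2/146) = 2.458. The 95% CI half-width is 1.96 × 2.458 = 4.8 points.
- Power = Φ(8/2.458 − 1.96) = Φ(1.295) = 90.2%.

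The SD of 21 comes from two reported SDs, 21.7 and 20.5, and nothing says that either is baseline-adjusted. The 90% therefore does not rely on adjusting for baseline OMAS.

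**Illustration of what baseline OMAS could add**

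The SAP gives no baseline to 6-month correlation, so r is assumed. With baseline OMAS as the only covariate, the residual SD is 21 × √(1 − r²). Omitting it inflates the SE by 1/√(1 − r²).

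| r (assumed) | SE inflation if omitted | CI half-width with baseline | Power with baseline |
|---|---|---|---|
| 0 | none | 4.8 | 90.2% |
| 0.2 | 2% | 4.7 | 91.3% |
| 0.3 | 5% | 4.6 | 92.7% |
| 0.5 | 15% | 4.2 | 96.4% |

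These rows compare adjustment for baseline with no adjustment at all. The 6.2.1 model already has centre, fracture management, age and sex. The actual gain depends on the partial correlation of baseline OMAS with the 6-month score given those covariates, which the SAP does not give.

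**Centre**

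With at least 20 centres (section 3.1), fixed centre effects use at least 19 degrees of freedom, leaving at most 292 − 2 − 19 = 271. The cost in power is small, but it is a different model from one with a random centre effect.

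**The case against.** The strongest reply is that the intention is clear from the rest of the document. A baseline outcome is needed for analysis, the CACE stage 2 model and the models described as similar to the primary one include the baseline score with centre random, and a partially adjusted model holding only baseline OMAS makes sense only if the full model holds it too. On this view a phrase dropped out of 6.2.1. That is the likeliest explanation, and it stands. It does not tell a programmer which text to follow on centre, nor whether age and sex belong.

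A reader might go further in several directions that the SAP does not support:

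- **That 6.2.1 prevails and the trial has decided to drop its most important covariate.** No precedence is stated, and no correlation is given from which to rank baseline OMAS among the covariates.
- **That the trial is underpowered as a result.** The planned 90% was computed without any stated covariate allowance and holds without baseline adjustment. Randomisation also means that the omission does not bias the estimate, and the baseline-adjusted sensitivity result is to appear in the same table.
- **That 6.2.2 enters centre twice, once as fixed.** The EQ-5D and PROMIS paragraphs contain no fixed-effect list. A random intercept is one way to adjust for centre, so the second mention can be repetition. The pain model separates the two plainly.
- **That the subgroup analysis abandons the mixed model.** The primary model is itself called a mixed-effects linear regression, so section 6.4 may be shorthand. The subgroup analysis is exploratory and has no p-values.
- **That fixed centre effects are wrong.** Fixed or random centre is a legitimate choice for the sponsor. The fault is that the SAP makes both.

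**Conclusion.** The inconsistency is real. Sections 3.8 and 6.2.1 differ on baseline OMAS, on age and sex, and on how centre enters, and nothing in the SAP resolves it. The main consequence is that the primary model is not uniquely pre-specified. The second is a possible loss of precision if 6.2.1 is followed literally: about 2%, 5% or 15% on the standard error for an assumed r of 0.2, 0.3 or 0.5. Those figures assume that SD 21 is unadjusted and that no other covariates are present; they are illustrative and not a prediction for this trial. The sample size reproduces, and planned power stays at 90%. The points on 6.2.2 and 6.4 are requests for clarification only.

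**What to change.** Write one primary model and put it in identical words in 3.8 and 6.2.1:

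- OMAS at 2, 4 and 6 months as the dependent variable, with a treatment-by-time interaction and the 6-month contrast as primary.
- Baseline OMAS, fracture management, age and sex as fixed effects.
- Centre entered once. Random fits 3.8, the CACE stage 2 model and the secondary models; if the sponsor prefers fixed, give the reason and align the other sections.
- The participant-level random effect or covariance structure for the repeated OMAS scores, named explicitly. Section 6.2.1 currently mentions only clustered standard errors for serial correlation.

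Then, in 6.2.2, say for EQ-5D and PROMIS that centre enters once, as the random effect. In 6.4, say that the subgroup interaction is added to this same primary model.

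The cost is SAP wording. Baseline OMAS is already collected, centre is already a randomisation factor, and neither the sample size nor data collection changes. The revision should be dated and made before treatment allocation is added to the analysis dataset.

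### The CACE text contradicts itself: one sentence makes treatment received the instrument for allocation, while the two stage models correctly use allocation to predict compliance

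*SAP*

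**What the plan says.** The CACE analysis is one of the sensitivity analyses of the primary outcome in SAP section 6.2.1. Compliance is at least four sessions: "Full compliance is defined as receiving a minimum of 4 physiotherapy sessions". Control-arm crossover is expected to be rare: "it is unlikely for participants in the control arm to crossover to the intervention arm".

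The estimator is described in this order:

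- The Stage 1 heading: "Stage 1: Predict treatment compliance using treatment allocated".
- The sentence at issue: "Treatment received (compliance) by participants will be used as an instrumental variable (IV) for treatment allocated".
- The Stage 1 model: "A mixed model, with the independent variable as treatment allocation and the dependent variable as treatment compliance, will run". Its covariates are the OMAS score at baseline and how the fracture was first managed.
- The prediction step: "The coefficient estimated for treatment allocation will be used to predict treatment compliance in both intervention and control arm".
- The Stage 2 heading, which says that predicted compliance is to stand in for allocation.
- The Stage 2 model: "dependent variable as OMAS scores and independent variable as predicted treatment compliance and follow-up timepoint interaction", with recruitment centre as a random effect and the same adjustment.
- The software remark: "The Stata command 'ivregress' can perform the two-stage analysis together".

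The section then places the CACE result in one table with the intention-to-treat and other sensitivity results, with 95% confidence intervals and p-values based on standard errors clustered for serial correlation.

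**The concern.** An instrument must be independent of prognosis. Randomised allocation is. Attending four or more sessions happens after randomisation and is partly the participant's choice, so it is not. The SAP contains one sentence that names an instrument, and it names the wrong variable.

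This matters because the SAP offers ivregress as a way to run both stages in one call. Whoever writes that call must state which variable is endogenous and which is the excluded instrument. Someone who takes this from the sentence obtains an estimate that carries the prognosis of attenders. The SAP introduces CACE because per-protocol exclusions may bias the estimate, so the literal coding would undo the purpose of the analysis. Section 7 also has a second statistician repeat the analyses independently, and two competent analysts could code this text differently.

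A smaller matter sits beside it. The stages are mixed models with a random centre effect, and ivregress fits no random effects. The SAP therefore leaves open which estimator, and which standard error, produces the reported CACE.

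**Working it through.** **Figures in the plan.** The SAP gives no numerical figure for the CACE. The planning values used below come from section 3.3: a target of 8 OMAS points, SD 21, and 292 evaluable participants at 90% power and 5% two-sided significance. A two-sample t calculation reproduces 146 per arm (power 0.9004; 145 per arm gives 0.8985). Nothing in this point depends on that calculation.

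**Direction of each statement**

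| Place in section 6.2.1 | Predictor | Predicted | Direction |
|---|---|---|---|
| Stage 1 heading | allocation | compliance | correct |
| Instrument sentence | compliance (as instrument) | allocation | reversed |
| Stage 1 model and prediction | allocation | compliance | correct |
| Stage 2 heading | predicted compliance, said to represent allocation | – | loose |
| Stage 2 model | predicted compliance | OMAS | correct |

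**Algebra for the literal reading.** Let Z be allocation (1:1, section 3.2), C indicate a would-be complier with probability p, and D = Z·C be treatment received, so that no control crosses over. Would-be compliers score s points better whatever their arm, and the true complier effect is t. Ignore covariates. Using D as the instrument for Z gives cov(Y,D)/cov(Z,D), where

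- cov(Z,D) = 0.5p − 0.5 × 0.5p = 0.25p
- cov(C,D) = 0.5p − p × 0.5p = 0.5p(1−p)
- var(D) = 0.5p(1−0.5p)
- cov(Y,D) = s·cov(C,D) + t·var(D)

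The estimate is therefore **t(2−p) + 2(1−p)s**. The second term is selection and the first is a rescaled true effect.

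With t = 0:

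- p = 0.7, s = 8: 2 × 0.3 × 8 = 4.8 points, or 4.8/8 = 60% of the target difference
- p = 0.8, s = 5: 2 × 0.2 × 5 = 2.0
- p = 0.6, s = 12: 2 × 0.4 × 12 = 9.6

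With t = 8 and p = 0.7: at s = 0 the estimate is 8 × 1.3 = 10.4, and at s = 8 it is 10.4 + 4.8 = 15.2.

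**Simulation.** Set-up: 292 participants, 1:1, residual SD 21, one 6-month outcome, no control crossover, two covariates unrelated to compliance, 2,000 replicates per scenario. Mean estimates:

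| p | s | true t | Stages 1 and 2 as linear regressions | Literal reversed instrument | Formula for reversed |
|---|---|---|---|---|---|
| 0.7 | 0 | 8 | 7.93 | 10.34 | 10.4 |
| 0.7 | 5 | 0 | −0.07 | 3.02 | 3.0 |
| 0.7 | 5 | 8 | 7.94 | 13.41 | 13.4 |
| 0.6 | 10 | 0 | 0.04 | 8.00 | 8.0 |
| 0.9 | 5 | 0 | −0.05 | 0.96 | 1.0 |

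Over the whole grid (p from 0.6 to 0.9, s of 0, 5 and 10) the two-stage regression averaged −0.14 to 0.09 when the truth was 0 and 7.83 to 8.08 when it was 8. It agreed with standard IV, allocation as instrument, to about 1e-12. These runs contained no centre effect or repeated visits. They check the direction and validity of the point estimate, not the exact mixed model or its standard errors.

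**Standard errors.** If the two stages are run separately, second-stage standard errors treat predicted compliance as known. The clustering that the SAP specifies deals with serial correlation, not with the estimated first stage.

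**The case against.** A reader might infer that the CACE section as a whole reverses the instrument, and that the planned CACE is therefore biased. The documents do not support this. The heading before the sentence and both models after it use allocation to predict compliance. A reversed analysis would predict allocation from compliance and regress OMAS on predicted allocation, and neither model appears. To reach the biased estimator an analyst would have to override both specified stages.

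The size can also be challenged, and much of that challenge stands. The SAP states neither p nor s. The upper value s = 12 exceeds the 8-point target. The formula ignores baseline OMAS and fracture management, which could absorb part of a prognostic gap. Nor is the whole inflation selection: at p = 0.7 and s = 0 a true effect of 8 already becomes 10.4.

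On the software, the SAP says only that ivregress can do the job. Centre could enter as indicators, since section 6.2.1 lists centre among the fixed effects of the primary model. That makes the mismatch resolvable, but the text does not resolve it.

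What survives is that the sentence is wrong, contradicts its neighbours, and is the only place where the SAP names an instrument.

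**Conclusion.** This is an internal contradiction to correct, of moderate severity. Under the usual IV assumptions, the models as described give valid point estimates. The bias is conditional on coding the sentence literally. It is then 2(1−p)s under a true null, that is 4.8 OMAS points at p = 0.7 and s = 8, with a range of 2.0 to 9.6, and a true effect is additionally multiplied by (2−p). These sizes assume no control crossover, no covariate adjustment, and values of p and s that are not in the SAP.

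Independently of the reversed sentence, the SAP does not fix one CACE estimator: ivregress is not equivalent to the mixed-model stages, and naive second-stage standard errors ignore first-stage estimation. CACE is a supporting sensitivity analysis, so the primary intention-to-treat result and the sample size are unaffected.

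**What to change.** 1. Replace the instrument sentence with: *Randomised allocation is the instrument for treatment received (compliance).*
2. Reword the Stage 2 heading to say that predicted compliance replaces treatment received.
3. Name one estimator and its standard errors. Either option is coherent:
   - joint two-stage least squares with ivregress: compliance endogenous, allocation the excluded instrument, centre as indicators, and robust or clustered standard errors from the joint fit. If all visits are pooled, each compliance-by-visit term needs its matching allocation-by-visit instrument;
   - the two-stage mixed model as now described, with standard errors from a bootstrap that repeats both stages.

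Removing the mixed-model Stage 2 is a choice, not a necessity; keeping it preserves the by-visit structure shared with the primary model. The cost is a few sentences of SAP text, plus a short bootstrap program if the second option is taken. No new data are needed.
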